### 8.8. Severity Assessment

If required on the AE CRFs, the investigator will use the adjectives MILD, MODERATE, or SEVERE to describe the maximum intensity of the AE. For purposes of consistency, these intensity grades are defined as follows:

MILD	Does not interfere with subject's usual function.
MODERATE	Interferes to some extent with subject's usual function.
SEVERE	Interferes significantly with subject's usual function.

Note the distinction between the severity and the seriousness of an AE. A severe event is not necessarily an SAE. For example, a headache may be severe (interferes significantly with the subject's usual function) but would not be classified as serious unless it met one of the criteria for SAEs, listed above.

### 8.9. Causality Assessment

The investigator's assessment of causality must be provided for all AEs (serious and non-serious); the investigator must record the causal relationship in the CRF, as appropriate, and report such an assessment in accordance with the SAE requirements if applicable. An investigator's causality assessment is the determination of whether there exists a reasonable possibility that the investigational product caused or contributed to an AE; generally the facts

(evidence) or arguments to suggest a causal relationship should be provided. If the investigator does not know whether or not the investigational product caused the event, then the event will be handled as “related to investigational product” for reporting purposes, as defined by the Sponsor (see the Section on [Reporting Requirements](#)). If the investigator's causality assessment is "unknown but not related to investigational product", this should be clearly documented on study records.

In addition, if the investigator determines that an SAE is associated with study procedures, the investigator must record this causal relationship in the source documents and CRF, as appropriate, and report such an assessment in accordance with the SAE reporting requirements, if applicable.

### **8.10. Exposure During Pregnancy**

For both unapproved/unlicensed products and for marketed products, an exposure during pregnancy occurs if:

1. A female becomes, or is found to be, pregnant either while receiving or having been exposed (eg, because of treatment or environmental exposure) to the investigational product; or the female becomes or is found to be pregnant after discontinuing and/or being exposed to the investigational product;

An example of environmental exposure would be a case involving direct contact with a Pfizer product in a pregnant woman (eg, a nurse reports that she is pregnant and has been exposed to chemotherapeutic products).

2. A male has been exposed (eg, because of treatment or environmental exposure) to the investigational product prior to or around the time of conception and/or is exposed during his partner's pregnancy.

If a study subject or study subject's partner becomes or is found to be pregnant during the study subject's treatment with the investigational product, the investigator must submit this information to the Pfizer SAE Triage Group, on an SAE report form and Exposure During Pregnancy (EDP) supplemental form, regardless of whether an SAE has occurred. In addition, the investigator must submit information regarding environmental exposure to a Pfizer product in a pregnant woman (eg, a subject reports that she is pregnant and has been exposed to a cytotoxic product by inhalation or spillage) using the EDP supplemental form. This must be done irrespective of whether an AE has occurred and within 24 hours of awareness of the exposure. The information submitted should include the anticipated date of delivery (see below for information related to termination of pregnancy).

Follow-up is conducted to obtain general information on the pregnancy and its outcome for all EDP reports with an unknown outcome. The investigator will follow the pregnancy until completion (or until pregnancy termination) and notify Pfizer of the outcome as a follow-up to the initial EDP supplemental form. In the case of a live birth, the structural integrity of the neonate can be assessed at the time of birth. In the event of a termination, the reason(s) for termination should be specified and, if clinically possible, the structural integrity of the

terminated fetus should be assessed by gross visual inspection (unless preprocedure test findings are conclusive for a congenital anomaly and the findings are reported).

If the outcome of the pregnancy meets the criteria for an SAE (ie, ectopic pregnancy, spontaneous abortion, intrauterine fetal demise, neonatal death, or congenital anomaly [in a live-born baby, a terminated fetus, an intrauterine fetal demise, or a neonatal death]), the investigator should follow the procedures for reporting SAEs.

Additional information about pregnancy outcomes that are reported as SAEs follows:

- Spontaneous abortion includes miscarriage and missed abortion;
- Neonatal deaths that occur within 1 month of birth should be reported, without regard to causality, as SAEs. In addition, infant deaths after 1 month should be reported as SAEs when the investigator assesses the infant death as related or possibly related to exposure to the investigational product.

Additional information regarding the EDP may be requested by the investigator. Further follow-up of birth outcomes will be handled on a case-by-case basis (eg, follow-up on preterm infants to identify developmental delays). In the case of paternal exposure, the investigator will provide the study subject with the Pregnant Partner Release of Information Form to deliver to his partner. The investigator must document in the source documents that the subject was given the Pregnant Partner Release of Information Form to provide to his partner.

### **8.11. Occupational Exposure**

An occupational exposure occurs when during the performance of job duties, a person (whether a healthcare professional or otherwise) gets in unplanned direct contact with the product, which may or may not lead to the occurrence of an adverse event.

An occupational exposure is reported to the Pfizer SAE Triage Group within 24 hours of the investigator's awareness, using the SAE Report form, regardless of whether there is an associated AE/SAE. Since the information does not pertain to a subject enrolled in the study, the information is not reported on a CRF, however a copy of the completed SAE Report form is maintained in the investigator site file.

### **8.12. Withdrawal Due to Adverse Events (See Also the Section on [Subject Withdrawal](#))**

Withdrawal due to AEs should be distinguished from withdrawal due to other causes, according to the definition of AE noted earlier, and recorded on the appropriate AE CRF page.

When a subject withdraws because of an SAE, the SAE must be reported in accordance with the reporting requirements defined below.

### **8.13. Eliciting Adverse Event Information**

The investigator is to report all directly observed AEs and all AEs spontaneously reported by the study subject. In addition, each study subject will be questioned about AEs.

### **8.14. Reporting Requirements**

Each AE is to be assessed to determine if it meets the criteria for SAEs. If an SAE occurs, expedited reporting will follow local and international regulations, as appropriate.

#### **8.14.1. Serious Adverse Event Reporting Requirements**

All SAEs will be reported on the AE eCRF (marked as serious) and on the Clinical Trial SAE report form (available in Firecrest) to be submitted to the Pfizer SAE Triage Group, within 24 hours of investigator's awareness. The form must be completed fully, including an assessment of SAE causality on the submitted forms (see [Section 8.9](#)). The Pfizer SAE Triage Group will identify potential disease-related efficacy endpoint SAEs as defined in [Section 8.6.1](#). The identified potential disease-related efficacy endpoints will not be reported into the Pfizer DSU unless the investigator believes there is a causal relationship between study drug and a potential disease-related efficacy endpoint. Other SAEs that are not potential disease-related efficacy endpoints will be reported to the DSU, by the Pfizer SAE Triage Group.

In particular, if the SAE is fatal or life-threatening, notification to the Pfizer SAE Triage Group must be made immediately, irrespective of the extent of available AE information. This time frame also applies to additional new information (follow-up) on previously forwarded SAE reports as well as to the initial and follow-up reporting of exposure during pregnancy, exposure via breastfeeding and occupational exposure cases.

If a potential disease-related efficacy endpoint SAE is subsequently adjudicated not to be an endpoint, the site will be contacted by the Adjudication Committee and asked to submit an updated SAE form. The form should be revised to show the awareness date (the date of notification by the Adjudication Committee). This form should be submitted to the Pfizer SAE Triage Group within 24 hours of the notification from the Adjudication Committee. This process is shown in [Appendix 9](#).

SAEs must be reported for all subjects (including screen failures) from the time of signing informed consent up to and including 40 days after discontinuing study drug, with this period, including events occurring between pre-screening (the time of pre-screening informed consent) and randomization.

For all SAEs, the investigator is obligated to pursue and provide information to Pfizer in accordance with the time frames for reporting specified above. Follow up information for previously forwarded SAE reports, should be reported directly to the DSU within 24 hours of investigator awareness. In addition, an investigator may be requested by Pfizer to obtain specific additional follow-up information in an expedited fashion. This information collected for SAEs is more detailed than that captured on the AE CRF. In general, this will include a description of the AE in sufficient detail to allow for a complete medical assessment of the

case and independent determination of possible causality. Information on other possible causes of the event, such as concomitant medications, vaccines, and/or illnesses, must be provided. In the case of a subject death, a summary of available autopsy findings must be submitted as soon as possible to Pfizer or its designated representative.

In the rare event that the investigator does not become aware of the occurrence of an SAE immediately (eg, if an outpatient study subject initially seeks treatment elsewhere), the investigator is to report the event to the Pfizer SAE Triage Group within 24 hours after learning of it and document the time of his or her first awareness of the SAE.

#### **8.14.2. Non-Serious Adverse Event Reporting Requirements**

All AEs will be reported on the AE page(s) of the CRF. It should be noted that the form for collection of SAE information is not the same as the AE CRF. Where the same data are collected, the forms must be completed in a consistent manner. For example, the same AE term should be used on both forms. AEs should be reported using concise medical terminology on the CRFs as well as on the form for collection of SAE information.

#### **8.14.3. Medical Device Complaint Reporting Requirements**

All medical device complaints, regardless of whether the medical device complaint is associated with an AE, will be collected on the applicable pages within the CRF. This includes potential incidents or malfunctions associated with the use of a medical device product. An incident or malfunction is an event that might have led to death or serious deterioration in health, or if it occurred again might have led to death or serious deterioration in health.

Pfizer is to be notified of all medical device complaints within 24 hours of the investigator's awareness of the event.

#### **8.14.4. Sponsor's Reporting Requirements to Regulatory Authorities**

Adverse event reporting, including suspected unexpected serious adverse reactions, will be carried out in accordance with applicable local regulations.

### **9. DATA ANALYSIS/STATISTICAL METHODS**

Detailed methodology for summaries and statistical analyses of the data collected in this study will be documented in a Statistical Analysis Plan (SAP), which will be maintained by the sponsor. This document may modify the plans outlined in the protocol; however, any major modifications of the primary endpoint definition and/or its analysis will also be reflected in a protocol amendment.

#### **9.1. Sample Size Determination**

A sample size estimate of 11,000 randomized subjects (5,500 on bococizumab and 5,500 on placebo) has approximately 90% power to detect a 25% reduction in the risk of experiencing the primary endpoint, by means of a two-sided  $\alpha=0.05$  log rank test. The required number of subjects with an adjudicated and confirmed event is 508. The sample size calculation is

based on an annual event rate of 2.7% and a premature study discontinuation rate of 1% per year. The trial is intended to complete after approximately 508 subjects have accrued an adjudicated and confirmed primary endpoint event (as defined in [Section 2.2.1](#)) or 12 months following the date that the last subject is randomized, whichever occurs later. Assuming that the trial will recruit in 2.5 years, with approximately 50% of the subjects in the last six months, the study will finish in another approximately 1.4 years for a trial duration of approximately 3.9 years.

The sample size may be modified to shorten the expected duration of the trial or to improve the likelihood of attaining 70% power for the key secondary composite endpoint of CV death, non-fatal MI and non-fatal stroke. Prior to the end of enrollment, blinded assessments will be made of the expected duration of the trial and of the power for this endpoint, assuming a hazard ratio (HR) of 0.75 at a two-sided alpha of 0.05. Under these assumptions, 299 confirmed and adjudicated events will provide approximately 70% power.

In addition, the sample size in certain subgroups, including diabetic subjects with no prior CVD event, may be modified or the trial duration may be extended to improve the likelihood that the estimated hazard ratios in the subgroups are less than one. Prior to the end of enrollment, the sponsor will perform a blinded assessment of the probabilities, assuming a hazard ratio of 0.75. Under this assumption, 35 events will provide approximately 80% probability that a point estimate is less than one.

As any adjustment to the sample size or duration of follow-up will be based on blinded data, the distribution of the test statistic for the primary analysis under the null hypothesis will not be affected and no alpha adjustment will be made.

These power and trial duration calculations were done with the software package EaST® (version 6.3.1).

### **9.1.1. Cognitive Testing Sample Size**

One of the objectives for this trial is to describe the safety of bococizumab and placebo with respect to assessments of cognitive testing. Cognitive testing will be performed at baseline (Visit 5), annually, and at the EDC and EOS visits at a subset of designated study sites in approximately 500 subjects (250/treatment group). This number of subjects is based on feasibility of sites with the appropriate staff and workspace to administer the testing accurately.

Assuming 80% of the 500 subjects will have cognitive testing performed at Visit 11 (Week 52) and 70% at Visit 14 (Week 104), it is expected that 400 subjects (200/group) will have cognitive testing at Week 52 and 350 subjects (175/group) at Week 104. Precision estimates are defined as the half-width of the 95% confidence interval for these assumed sample sizes at Week 52 and Week 104 for each cognitive test and are displayed in the table below.

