**Table 3. Precision Estimates for Cognitive Assessments**

Cognitive Test	Visit	N/group	SD*	Precision
Digit Span (Forward)	Week 52	200	2	±0.39
	Week 104	175	2	±0.42
Digit Span (Backward)	Week 52	200	2	±0.39
	Week 104	175	2	±0.42
Digit Symbol Substitution Test	Week 52	200	9	±1.76
	Week 104	175	9	±1.89
Trail Making A	Week 52	200	22	±4.31
	Week 104	175	22	±4.61
Trail Making B	Week 52	200	40	±7.84
	Week 104	175	40	±8.38
HVLTL Learning	Week 52	200	4	±0.78
	Week 104	175	4	±0.84
HVLTL Delayed Recall	Week 52	200	2	±0.39
	Week 104	175	2	±0.42

\*Based on data for cognitively normal subjects from the Alzheimer’s Disease Neuroimaging Initiative (ADNI) study except for HVLTL which is based on data for placebo subjects from Pfizer Study A4091004

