Observations of potential clinical concern after the first dose of study medication for hematology, blood chemistry and all urinalysis parameters will be tabulated by treatment group as categorical variables according to sponsor standards. Subjects meeting one or more criterion for Hy's Law will be tabulated by treatment group according to sponsor standards.

The maximum post-randomization total bilirubin value will be plotted against the maximum post-randomization alanine transaminase (ALT) value (Evaluation of Drug-Induced Serious Hepatotoxicity [eDISH] plot).

Electrocardiograms

12-lead ECGs will be locally read and the interpretations will be kept at the investigation sites as source documents. Any clinically significant ECG abnormalities will be reported as AEs. As a result of the discontinuation of the bococizumab clinical development program, ECG data will not be summarized or listed.

Physical and neurological exams

As a result of the discontinuation of the bococizumab clinical development program, physical examination findings will not be listed. Also, neurological exam findings will not be summarized or listed.

Cognitive Tests

Changes from baseline in cognitive test results, including the Digit Span Forward score, Digit Span Backward Score, Digit Symbol - Coding score, Trail Making A score, Trail Making B score, HVLT Total Recall score, HVLT Delayed Recall Trial score, and the HVLT Recognition score will be analyzed using an MMRM model. The fixed effects will be treatment group (categorical variable), scheduled visit time point (categorical variable), baseline value (continuous variable), interaction between baseline value and scheduled visit time point and interaction between treatment and scheduled visit time point. REML estimation will be used and the default covariance structure will be unstructured. Due to the slow onset of accrual in this event-driven trial, there will be few observations at the last several time points. One or more of the last visits may be removed to ensure convergence of the model fitting. If the model fitting fails to converge, compound symmetry will be used as the covariance structure. Consistent with MMRM model fitting, no explicit imputation of missing assessments will be performed. Estimates of treatment group means and mean treatment group differences at each visit along with corresponding 95% confidence intervals will be provided. The confidence intervals are for estimation purposes only.

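### Protocol Table 3's Week 104 cognitive precision rests on 175 tested per group, which the accrual and duration plan in Section 9.1 does not support

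*Protocol*

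**What the plan says.** Protocol Section 9.1.1 sets a cognitive subset of about 500 subjects (250 per group), a size chosen for site feasibility. It assumes that 80% are tested at Week 52 and 70% at Week 104, so that "it is expected that 400 subjects (200/group) will have cognitive testing at Week 52 and 350 subjects (175/group) at Week 104". It adds: "Precision estimates are defined as the half-width of the 95% confidence interval". Table 3, "Precision Estimates for Cognitive Assessments", gives Week 104 values of ±0.42 (SD 2), ±0.84 (SD 4), ±1.89 (SD 9), ±4.61 (SD 22) and ±8.38 (SD 40).

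Protocol Section 9.1 gives the calendar for the whole trial. Recruitment takes 2.5 years and, "with approximately 50% of the subjects in the last six months, the study will finish in another approximately 1.4 years", for a total of about 3.9 years. Premature study discontinuation is put at 1% per year.

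Footnote 6 of the Schedule of Activities restricts cognitive testing to designated US and Canadian sites. Testing is at baseline, annually, and at early discontinuation or end of study (EOS). No accrual calendar is given for this subset.

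SAP Section 8.2.3 (Cognitive Tests) says: "Due to the slow onset of accrual in this event-driven trial, there will be few observations at the last several time points". It allows late visits to be dropped from the model. SAP Appendix 1.1, Table 4, assigns cognitive tests on study days 666 to 791 to Week 104.

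**The concern.** Subjects randomized in the last six months of recruitment have between 1.4 and 1.9 years of follow-up when the study closes at year 3.9, or about 73 to 99 weeks. On the Section 9.1 calendar none of them reaches Week 104, or Week 102 at the early edge of the ±14-day visit window. They are about half of the trial. An expectation that 70% of a subset will be tested at Week 104 therefore needs a reason why the subset differs from the trial, and no reason is given.

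Describing cognitive safety is a stated objective, and Table 3 is the only statement of how precisely the trial will do so. If its Week 104 N is too large, a reader expects narrower two-year intervals than the design provides.

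**Working it through.** **1. Reproduce Table 3.** The half-width for a difference of two means is 1.96 × SD × √(2/n).
- n = 200: 0.392 (SD 2), 0.784 (SD 4), 1.764 (SD 9), 4.312 (SD 22), 7.840 (SD 40).
- n = 175: 0.419, 0.838, 1.886, 4.610, 8.381.

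Every entry matches after rounding. The formula is right; the question is the Week 104 n.

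**2. Latest randomization that reaches Week 104.** 104 weeks = 728 days = 728/365.25 = 1.993 years. 3.9 − 1.993 = year 1.907 of recruitment.

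**3. Share randomized by then.** Section 9.1 gives 50% by year 2.0 but not the shape of accrual before that, so two shapes are assumed.
- Uniform over years 0 to 2: 0.5 × (1.907/2) = 47.7%.
- Back-loaded, density proportional to t²: 0.5 × (1.907/2)³ = 43.3%.

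**4. Dropout at 1% per year.** 0.99^1.993 = 0.980.
- Uniform: 0.477 × 0.980 = 46.7%; × 250 = about 117 per group.
- Back-loaded: 0.433 × 0.980 = 42.5%; × 250 = about 106 per group.

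**5. Allow EOS tests through SAP Table 4.** Day 666 is 665 days after first dose, or 1.821 years, so with EOS at year 3.9 entry must be by year 2.079. Taking accrual as uniform in years 2.0 to 2.5 (assumed), the share is 0.5 + 0.079 = 57.9%. After dropout (0.99^1.821 = 0.982) it is 56.9%, or about 142 per group. The documents give no interval between the stopping date and EOS visits. Assumed lags of 4 and 8 weeks give 64.4% (161 per group) and 71.9% (180 per group).

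**6. Week 104 half-widths.**

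| Scenario | n/group | SD 2 | SD 4 | SD 9 | SD 22 | SD 40 | Width vs Table 3 |
|---|---|---|---|---|---|---|---|
| Table 3 | 175 | 0.42 | 0.84 | 1.89 | 4.61 | 8.38 | – |
| Week 104, uniform | 117 | 0.51 | 1.03 | 2.31 | 5.64 | 10.26 | +22% |
| Week 104, back-loaded | 106 | 0.54 | 1.08 | 2.42 | 5.92 | 10.76 | +28% |
| EOS from day 666, no lag | 142 | 0.46 | 0.93 | 2.09 | 5.11 | 9.30 | +11% |
| EOS from day 666, 4-week lag | 161 | 0.44 | 0.87 | 1.97 | 4.81 | 8.74 | +4% |
| EOS from day 666, 8-week lag | 180 | 0.41 | 0.83 | 1.86 | 4.55 | 8.27 | −1% |

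The last column is √(175/n) − 1. All recomputed rows lose subjects only to closure and 1% per year dropout; nobody misses a test. In the 8-week row, 175 is kept only if missed tests stay below about 3% (175/180 = 0.97).

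**7. What 70% at Week 104 itself would need.** 0.70/0.980 = 71% of the subset randomized by about year 1.9. Alternatively, under the whole-trial profile, entry counted to year 2.214 (0.5 + 0.214 = 0.714) gives a trial of 2.214 + 1.993 = about 4.2 years.

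**8. Week 52.** Minimum follow-up is about 1.4 years (73 weeks), so closure removes nobody and those rows stand.

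**The case against.** The strongest reply is that Section 9.1 describes 11,000 subjects, while the subset is about 500 at designated US and Canadian sites whose accrual is not given. If some 71% of them entered by about year 1.9, the stated 70% is attainable. The trial is also event-driven and may be extended. Both points stand. A reader might infer that 175 per group cannot be delivered, and the documents do not prove that. They do leave the 70% without support.

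A reader might also take half the subset, about 125 per group, as a ceiling. SAP Table 4 defeats that, because EOS tests from day 666 can be analysed as Week 104.

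A third inference is to apply the 70% as a testing rate on top of closure, giving about 85 per group. Section 9.1.1 states 70% as the share of the 500 who will be tested and does not say that it excludes closure, so this risks discounting twice. Some missed tests are still likely: the plan assumes only 80% at Week 52, where closure plays no part.

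It is also tempting to argue that the stop on 01 November 2016 leaves almost no subject with both a baseline and a Week 104 Hopkins Verbal Learning Test (HVLT), since Amendment 1 of 01 October 2014 added that test. In the SAP that date limits events sent for adjudication and the censoring of clinical endpoints. SAP Section 6.2 keeps all safety observations after first dose, and enrolment by date is not given. Dropping the HVLT at Week 104 is unsupported.

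Finally, the intervals are for estimation only, the observed model-based intervals will replace Table 3, and a model that adjusts for baseline and uses other visits will not follow the Table 3 formula exactly. That limits the consequence but does not correct the stated figure. The SAP remark on few late observations points the same way, though it does not name Week 104.

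**Conclusion.** The point holds as a mismatch between two parts of the protocol. Table 3's arithmetic is correct for 175 per group, but that N does not follow from the accrual and duration in Section 9.1, and no text bridges the gap. Assuming the subset accrues like the trial and the study closes at year 3.9, Week 104 half-widths are 22% to 28% wider than stated, or about 11% wider if EOS tests at year 3.9 count. The stated precision returns only with EOS visits about 8 weeks later and almost no missed tests, or with an early-enrolling subset or a longer trial that the protocol does not describe.

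The effect is confined to a descriptive safety precision. Singling out Week 52 as the visit that must carry the cognitive conclusion would be a preference and does not follow from this point.

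**What to change.** Recompute the Week 104 N and half-widths in Table 3 from the Section 9.1 accrual and duration. Alternatively, state an accrual schedule for the cognitive subset that supports 70%, and keep the present rows. In either case, say whether EOS tests falling in the SAP Table 4 window count toward Week 104, and use the same rule for the N in Table 3. In the analysis, report the number available at Week 104 for every cognitive test, including the HVLT.

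The cost is a few revised table rows and one or two sentences in the protocol and SAP, with no added subjects or tests. Unless the subset's schedule supports 70%, the stated two-year precision becomes less favourable.
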